9.1.4 Selection of the Index knee

For subjects who present with two potentially eligible knees at Screening it will be necessary to identify which knee is the Index knee (the Index knee is the knee in which IMP/vehicle control is to be administered and all efficacy and safety assessments are performed from Visit 2 onwards).

Selection of the Index knee will occur prior to randomisation at Visit 2, following final review of all eligibility criteria. To aid the sites in their review of eligibility criteria and selection of the Index knee, the ePRO devices will provide a summary of the Washout and Baseline diary entries for each knee, including (at minimum) the number of daily and weekly pain recordings and the Weekly WOMAC Pain scores. The criteria in [Table 6](#) below will be used to help select the Index knee.

If both knees meet all the criteria for the Index knee and do not exceed the maximum permitted WOMAC Pain subscale scores for the non-Index knee, then the worst knee is selected as the Index knee. If the WOMAC Pain scores are the same in both knees, the Investigator may select either knee as the Index knee in consultation with the Subject.

Table 6 Criteria for Selecting the Index knee in Subjects with a Diagnosis (or Symptoms) of Bilateral Knee OA at Screening

Criteria	Index Knee	Non-Index Knee
Diagnosis of primary OA of the knee (per ACR clinical and radiological criteria)	Required	Not required
	AND	AND
Subject reports OA symptoms present at least 6 months prior to Screening	Required	Not required
	AND	AND
Kellgren- Lawrence Grade	2 or 3	Not required
	AND	AND
Both WOMAC Pain subscale scores in the Washout & Baseline Period	≥ 4.0 to ≤ 9.0 (out of 10) and do not vary by >3 points	≤ 6.0 (out of 10)

Notes: ACR=American College of Rheumatology; OA=osteoarthritis; WOMAC=Western Ontario and McMaster Universities Osteoarthritis Index

9.1.5 Safety Assessments

Safety will be assessed through AE reporting, vital signs, clinical laboratory evaluations, and physical/knee examinations.

During the study, all clinical events spontaneously reported by the subject, observed by site staff or elicited by general questioning will be reported in the eCRF. Subjects will be questioned on their health status at each visit. Open-ended questions will be asked to elicit information about AEs (see [Section 10](#) for details).

The Investigator will receive and review the laboratory results for all subjects at their site and will review the data for all other assessed safety variables.

9.1.5.1 Clinical Laboratory Assessments

Detailed instructions on the collection, processing, handling and shipping of laboratory samples will be provided in the Laboratory Manual.

Blood samples will be analyzed for the following:

- Hemoglobin, hematocrit, erythrocytes (RBC), leukocytes (WBC), WBC differential (including total lymphocyte count and absolute neutrophil count), platelets
- HbA1c at Screening and Week 24 (End-of-Study/Early Exit Visit) only
- Alkaline phosphatase (ALP), ALT, AST, bicarbonate, bilirubin (total), blood urea nitrogen (BUN), chloride, creatinine, glucose (non-fasting), potassium, protein (total), sodium, uric acid
- Serum cortisol (see Section 9.1.5.1.1 below)

Urine samples will be analyzed for the following:

- pH, specific gravity, protein, glucose, ketones, bilirubin, hemoglobin, leukocytes, nitrite

Imaging Sub-Study

For subjects participating in the imaging sub-study, the most recent creatinine result will be used to calculate eGFR to confirm eligibility for MRI, e.g.:

- Visit 2: eGFR is calculated using the Screening Visit creatinine value.
- Visit 7: eGFR is calculated using either the Visit 6 or Visit 7 creatinine value.
- Visit 9: eGFR is calculated using either the Visit 8 or Visit 9 creatinine value.
- Visit 10: eGFR is calculated using the Visit 9 creatinine value

Estimated GFR will be calculated using the Chronic Kidney Disease Epidemiology Collaboration (CKD-EPI) equation ([Levey, et al., 2009](#)).

The clinical significance of out-of-range clinical laboratory findings will be determined and documented by the Investigator (or sub-Investigator).

9.1.5.1.1 Serum Cortisol

Blood samples for serum cortisol must be collected in the morning between 7 a.m. and 11 a.m. (exception: the ACTH stimulation test performed during Screening may be performed at any time of day).

During Screening, serum cortisol results from the samples collected during the ACTH stimulation test will be reported directly to the site for eligibility evaluation purposes.

Following randomization (Visit 2 onwards), serum cortisol results and ACTH stimulation test results will not be reported to the sites. Results will be reported separately to the Medical Monitor for review. See Section [6.2](#).

9.1.5.1.2 ACTH Stimulation Test

The ACTH stimulation test measures the ability of the adrenal cortex to respond to ACTH by appropriately producing cortisol. It is used to help diagnose adrenal insufficiency (AI).

The ACTH stimulation test involves the following steps (full details will be provided in the Laboratory Manual). Subjects are not required to be fasting for this test. The ACTH stimulation test may be performed at any time of day.

The procedure for the ACTH test is as follows:

- A baseline blood sample will be collected to measure serum cortisol and ACTH
 - If the ACTH stimulation test occurs on a scheduled visit where a morning serum cortisol sample is already being collected between 7 and 11 a.m., only a baseline blood sample for the measurement of ACTH is required.
- Inject the provided cosyntropin into the subject's shoulder muscle
- 30 minutes (± 5 minutes) post-injection, collect a blood sample to measure serum cortisol
- 60 minutes (± 5 minutes) post-injection, collect a blood sample to measure serum cortisol

The test will be performed in the following circumstances:

- **Visit 1a – Visit 1b** (Screening) in all subjects
 - This is to identify subjects with existing, undiagnosed AI, so they can be excluded from the study.
- If the subject's **Visit 6** (Week 8) serum cortisol is <350 nmol/L (<12.7 μ g/dL), perform the ACTH stimulation test at **Visit 7** (Week 12)
 - This is intended to identify if a subject with serum cortisol levels at the lower end of the normal range has developed asymptomatic AI in response to peak exposures of EP-104IAR.
 - If the subject's **Visit 7** (Week 12) ACTH stimulation test is abnormal, repeat the ACTH stimulation test at **Visit 9** (Week 24/End-of-Study/Early Exit Visit).
- If the subject's **Visit 9** (Week 24/End--of--Study/ Early Exit Visit) serum cortisol is <350 nmol/L (<12.7 μ g/dL), perform the ACTH stimulation test at an **Unscheduled Visit**
 - This is intended to identify if a subject with serum cortisol levels at the lower end of the normal range has developed slow developing asymptomatic AI in response to EP-104IAR administration, as it can take several weeks for AI to develop following adrenal atrophy.

- Not required if the subject has already completed an ACTH test at Visit 9 due to an earlier abnormal ACTH result.
- If the subject's serum cortisol is ≤ 138 nmol/L (≤ 5 μ g/dL) at **any visit** after dose administration **AND** they experience signs and symptoms of AI (see Section 10.2.5), perform the ACTH stimulation test at the **next scheduled visit**.

See [Figure 2](#) below.

During Screening, sites will receive serum cortisol results from the ACTH stimulation test directly from the central safety laboratory to determine subject eligibility. At all later timepoints serum cortisol results will be received by the unblinded Medical Monitor, who will inform the site which subjects should undergo the ACTH stimulation test. ACTH stimulation test results will be reported to the unblinded Medical Monitor for review.

[figure not shown]
Criteria for evaluating if the ACTH stimulation test response is normal or abnormal are provided in the Laboratory Manual.

If the results of the ACTH stimulation test are considered to be abnormal and the subject also displays symptoms of adrenal suppression, they should be managed accordingly and may require glucocorticoid replacement therapy (e.g., with physiologic hydrocortisone). If appropriate, such subjects should be referred to an Endocrinologist (or other appropriate specialist) for further evaluation and treatment.

The ACTH stimulation test is extremely sensitive (95% sensitivity and 97% specificity); however, this translates to a false positive result in approximately 1 out of every 20 tests. The ACTH stimulation test will be repeated at the End-of-Study Visit in any subjects with an abnormal test result at Week 12.

Subjects who are diagnosed with AI following dose administration should be managed by their Endocrinologist (or other appropriate specialist) until resolution. If the subject's AI is ongoing at their final scheduled study visit, the Investigator should follow-up with the subject approximately 3 months later, with at least 1 additional contact during that 3-month period.

Figure 2 Triggers for ACTH Stimulation Testing

Note: ACTH=Adrenocorticotrophic hormone Wk=Week.

Protocol No. EP-104IAR-201 - Version 7.0
15 Aug 2022

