11 A serum pregnancy test will be performed on all women of childbearing potential at Screening. The sample collected for clinical chemistry analysis may be used for this purpose. A urine pregnancy test will be performed on all women of childbearing potential at Visit 2 and the End-of-Study (or Early Exit) visit. If the subject is participating in the optional imaging sub-study, the Visit 2 urine pregnancy test will be performed prior to performing the MRI. It does not need to be repeated prior to dosing.

12 HbA1c will be measured at Screening and End-of-Study (or Early Exit) visits.

13 To be collected at approximately the same time each visit, between 7-11 a.m. The clinical chemistry sample can be used for cortisol analysis, if being collected at the same visit.

14 Prior to and 2 hours after dosing. (For the 2 hour post-dose assessment a -15/+15-minute window is permitted.)

15 The ACTH stimulation test may be performed at any time of day and on any day during Screening, including at Visit 1b.

16 If the morning serum cortisol test result at Visit 6 (Week 8) is <350 nmol/L (<12.7 µg/dL) an ACTH stimulation test is to be performed at Visit 7 (Week 12). The site will be notified of this requirement in advance of the subject attending this visit.

17 For subjects whose ACTH stimulation test was abnormal at Visit 7, the test will be repeated at the End-of-Study (or Early Exit) Visit (the site will be notified of this requirement in advance of the subject attending this visit).

18 For those subjects not undergoing the ACTH stimulation test at Visit 9 (Week 24/Early Exit) if the result of the morning serum cortisol test at this visit is <350 nmol/L (<12.7 µg/dL), the site will be informed that an unscheduled visit is required to perform an ACTH stimulation test.

Notes:
ACTH=Adrenocorticotrophic hormone; AEs=Adverse events; Chem=Blood chemistry panel; Commed=Concomitant medication; ePRO=Electronic patient-reported outcome; Hem=Blood hematology panel; MDGA=Physician's Global Assessment of Arthritis; MRI=Magnetic resonance imaging; NPRS=Numerical pain rating scale; OA=Osteoarthritis; PK=Pharmacokinetic; PIgA=Patient's Global Assessment of Arthritis; SF-36=Short Form 36 questionnaire; WOMAC=Western Ontario and McMaster Universities Osteoarthritis Index.

IMAGING SUB-STUDY ADDITIONAL SCHEDULE OF EVENTS

Visit	1a Screening (Multiple days)	2 Baseline & Dosing	7	9 End-of-Study (or Early Exit Visit)	10 Imaging Follow-up
Study Week	-8 to -3	1	12	24	52

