2.2 Risks/Precautions

Commonly reported local adverse effects of IA corticosteroid injection include IA and periarticular calcifications, cutaneous atrophy, and cutaneous depigmentation ([Habib, et al., 2010](#)).

Reported systemic effects of IA corticosteroid injection include flushing, hypothalamic-pituitary-adrenal axis suppression, transient increase in blood glucose levels in diabetics, decrease in serum inflammatory markers and cytokines, decrease in blood mononuclear cells and an increase in polymorphonuclear leukocytes, decrease in plasma viscosity, anaphylaxis and allergic reactions, and infections ([Habib, 2009](#)). As a precaution, insulin-dependent and poorly controlled non-insulin-dependent diabetics, individuals with current or recent infections and individuals with abnormal laboratory test findings (as defined in the exclusion criteria, Section [5.3](#)) will be excluded from this study.

EP-104IAR animal studies identified the adrenal glands and the liver as target organs for EP-104IAR toxicity, consistent with systemic FP exposure. As a precaution, individuals with impaired liver function (as defined in the exclusion criteria, Section [5.3](#)) will be excluded from this study.

Animals with higher plasma levels of FP experienced reversible cortisol suppression. A similar finding was also observed in the Phase 1 clinical study. While the serum cortisol suppression observed in the Phase 1 study was transient and reversible, due to the higher dose of EP-104IAR being evaluated in this study, individuals with, or at greater risk of developing adrenal insufficiency (AI) will be excluded from participating in this study (see Section [5.3](#)). During the study, serum cortisol will be monitored closely by the Medical Monitor and while the dose of EP-104IAR selected for evaluation in this study is not anticipated to have any adverse effects on adrenal function, as an additional precautionary step, adrenocorticotrophic hormone (ACTH) stimulation testing will be performed, according to the criteria defined in Section [9.1.5.1.2](#). Subjects will be closely monitored for clinical signs and symptoms of AI and managed accordingly (see Section [10.2.5](#)). Finally, subjects will also be instructed to carry a wallet card identifying the potential risk for AI as a result of participating in the clinical study, and the potential need for emergency glucocorticoid therapy in the setting of shock, surgery, etc.

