In addition to the scheduled SRMs, safety data will be continuously reviewed by the Medical Monitor for trends or findings of concern. The Medical Monitor may request the SRC be reconvened at any time to review new safety findings and determine if the study should continue to enrol subjects.

Examples of reasons to reconvene the SRC include (but are not limited to):

- An AE of severe, persistent pain in the Index knee in an EP-104IAR-treated subject that is out of proportion with the subject's degree of OA and not otherwise explained by any other cause (e.g., injury or infection)
- Increased Index knee pain out of proportion with the subject's degree of OA, in combination with all of the following: redness, warmth, extensive swelling, 2+ effusion (upon stroke test), that are not explained by any other cause, in an EP-104IAR-treated subject
- The occurrence of an infection in the Index knee without another known cause
- The occurrence of a suspected unexpected serious adverse reaction (SUSAR) in an EP-104IAR-treated subject
- The occurrence of confirmed symptomatic adrenal insufficiency in >1 EP-104IAR-treated subject

Recommendations following review of new safety data by either the Medical Monitor or the SRC may include (but are not limited to): pausing enrollment to permit further evaluation of data; scheduling an additional planned review of data once further subjects have been dosed; amending the protocol to exclude subjects at potentially greater risk; or stopping enrollment (terminating the study early).

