7.6.1 Procedures for Overdose

Overdose should not be possible as each vial of EP-104IAR only contains a small overage to account for residual suspension remaining in the vial and syringe. However, if the intended dose results in extreme local or systemic symptoms, the Investigator should lavage the Index knee with saline and aspirate to remove as much EP-104IAR as possible.

Overdosage of corticosteroids may result in signs/symptoms of hypercorticism. Subjects should be observed carefully for any evidence of systemic corticosteroid effects. Particular care should be taken in observing subjects postoperatively or during periods of stress for evidence of inadequate adrenal response. It is possible that systemic corticosteroid effects such as hypercorticism and adrenal suppression (including adrenal crisis) may appear in a small number of patients who are sensitive to these effects. If such effects occur, accepted procedures for the management of symptoms should be followed (e.g., treatment with physiologic hydrocortisone, etc.).

Subjects will be instructed to carry a wallet card identifying the potential risk for AI as a result of participating in the clinical study, and the potential need for emergency glucocorticoid therapy in the setting of shock, surgery, etc.

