9.2.7 Unscheduled Visits

Unscheduled visits may be performed at the Investigator's discretion if there are safety findings of concern at scheduled visit assessments or reported by subjects between visits.

An unscheduled visit should also be performed in the following circumstances:

- **All subjects** - If the subject requires additional rescue medication between scheduled visits, they may call the site to obtain an additional bottle of rescue medication.
- **All subjects** - If at any time during the study a subject independently reports symptoms indicative of an infection in the Index knee (e.g., a red and swollen knee with moderate or large effusion, or a hot and swollen knee with a moderate or large effusion), a blood sample will be collected for hematology testing and the subject should be referred for further specialist assessment as soon as possible.
- **Subjects with abnormal ACTH stimulation test results** - If the ACTH stimulation test performed at Visit 9 (Week 24/End-of-Study/Early Exit) is abnormal (as per the unblinded Medical Monitor's assessment), the subject should be asked to return to the site for a repeat test to confirm the initial result and additional safety evaluations, as required.
- **Subjects with abnormal serum cortisol test results** – If the serum cortisol test at Visit 9 (Week 24/End-of-Study/Early Exit) is abnormal as per the unblinded Medical Monitor's assessment (and the subject did not already complete an ACTH stimulation test at that visit), the subject should be asked to return to the site to complete an ACTH stimulation test.
- **Subjects who withdraw early** – If a subject withdraws early from the study and their most recent visit serum cortisol was <350 nmol/L (<12.7 µg/dL) (as per the unblinded Medical Monitor's review) the subject should be asked to return to the site for an ACTH stimulation test and additional safety evaluations, as required.

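### For a dosed subject with cortisol of 138 nmol/L or lower and symptoms of adrenal insufficiency at Visits 3 to 8, the protocol's only explicit timing for the ACTH test is the next scheduled visit, nominally up to 12 to 42 days away

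*Protocol*

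**What the plan says.** Section 9.1.5.1.2 of the protocol lists when an ACTH stimulation test is done. After dosing, the relevant triggers are:

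- Visit 6 cortisol below 350 nmol/L, without regard to symptoms: test at Visit 7. An abnormal Visit 7 result is repeated at Visit 9.
- Visit 9 cortisol below 350 nmol/L: test at an unscheduled visit. Footnote 18 of the Schedule of Events agrees: "the site will be informed that an unscheduled visit is required to perform an ACTH stimulation test".
- Cortisol of 138 nmol/L or lower at any post-dose visit, together with clinical features of AI. Here the text is "they experience signs and symptoms of AI (see Section 10.2.5), perform the ACTH stimulation test at the next scheduled visit".

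Other sections bear on the third case:

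- Section 10.2.5 asks for a cortisol sample when AI is suspected, with an ACTH test to follow if indicated. It gives no time for either.
- Section 9.2.7 says "Unscheduled visits may be performed at the Investigator's discretion if there are safety findings of concern". Its list of cases that call for a return visit does not include this trigger. One case it does include begins "If a subject withdraws early from the study and their most recent visit serum cortisol was <350 nmol/L".
- Sections 6.2 and 9.1.5.1.1 keep post-randomization cortisol results from the sites. The Medical Monitor reviews them and contacts the Investigator about confirmatory testing or management if required.
- ACTH footnotes 15 to 18 of the Schedule of Events do not mention the symptomatic trigger.

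**The concern.** Low cortisol together with symptoms is the clearest warning of AI among the cortisol-based triggers. Exclusion criterion 26 treats 138 nmol/L or lower at Screening as disqualifying even without symptoms. Yet the one timing instruction for this combination carries no urgency. Because sites cannot see the cortisol value, they depend on the Medical Monitor for half of the trigger, and the instruction that the Medical Monitor would apply points to the next scheduled visit.

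At stake is the speed of confirmation. Two later steps depend on it. Section 10.2.5 ties specialist referral to confirmed AI. One of the examples in Section 4.3 for reconvening the safety review committee (SRC) is "The occurrence of confirmed symptomatic adrenal insufficiency in >1 EP-104IAR-treated subject". No efficacy analysis is affected.

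**Working it through.** The protocol states no waiting time, so there is no figure of its own to reproduce. The inputs are the visit days and windows in Sections 9.2.5.1 to 9.2.5.7: Visit 3, Day 3 ±1; Visit 4, Day 15 ±3; Visit 5, Day 29 ±3; Visit 6, Day 57 ±3; Visit 7, Day 85 ±3; Visit 8, Day 127 ±3; Visit 9, Day 169 ±7. Cortisol is drawn at each of these visits.

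**Step 1: which visits matter.** A subject at or below 138 nmol/L at Visit 9 also meets the below-350 rule and gets an unscheduled test. The delay therefore concerns low samples at Visits 3 to 8.

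**Step 2: length of the wait.**
- Nominal = next visit day − current visit day.
- Shortest = earliest next day − latest current day.
- Longest = latest next day − earliest current day.

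| Low sample | Test at | Nominal | Shortest | Longest |
|---|---|---|---|---|
| Visit 3 | Visit 4 | 15−3 = 12 | 12−4 = 8 | 18−2 = 16 |
| Visit 4 | Visit 5 | 29−15 = 14 | 26−18 = 8 | 32−12 = 20 |
| Visit 5 | Visit 6 | 57−29 = 28 | 54−32 = 22 | 60−26 = 34 |
| Visit 6 | Visit 7 | 85−57 = 28 | 82−60 = 22 | 88−54 = 34 |
| Visit 7 | Visit 8 | 127−85 = 42 | 124−88 = 36 | 130−82 = 48 |
| Visit 8 | Visit 9 | 169−127 = 42 | 162−130 = 32 | 176−124 = 52 |

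These waits assume that symptoms are already present when the scheduled sample is drawn and that no other route is used. They are shorter if symptoms start later or the low sample is drawn between visits.

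**Step 3: comparison at Visit 6.** An asymptomatic subject below 350 nmol/L is tested at Visit 7, nominally 28 days on. A symptomatic subject at or below 138 nmol/L is also tested at Visit 7. The more serious trigger brings no earlier test.

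**Step 4: what a 7-day limit would gain.** Days saved = nominal wait − (7 + T), where T is the time from the sample until both parts of the trigger are known. The documents do not give T; I assume 0 to 5 days.

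| Low sample at | Saved, T = 0 | Saved, T = 5 |
|---|---|---|
| Visit 3 | 12−7 = 5 | 12−12 = 0 |
| Visit 4 | 14−7 = 7 | 14−12 = 2 |
| Visits 5, 6 | 28−7 = 21 | 28−12 = 16 |
| Visits 7, 8 | 42−7 = 35 | 42−12 = 30 |

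Most of the gain is at Visits 5 to 8.

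**The case against.** The strongest reply is that the symptomatic case is covered elsewhere. The rule itself refers to Section 10.2.5, which applies whenever AI is suspected and is not tied to a scheduled visit. Section 9.2.7 permits unscheduled visits, and Section 6.2 has the Medical Monitor contact the Investigator. On that reading the rule is a minimum. This stands in part: an earlier test is allowed, so the waits above are close to an upper bound. But none of these routes requires the test or gives a time, and nothing says that they override the stated timing.

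Waiting also has some rationale in the first weeks. In Phase 1 (Section 1.2.2), two subjects had cortisol falls of more than 75%; one recovered by one week and the other by three. Section 9.1.5.1.2 adds, of the Visit 9 test, "as it can take several weeks for AI to develop following adrenal atrophy". This argument weakens from Visit 5 (Week 4) on, where the waits are longest.

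The blind is a fair point too. Section 6.2 relies on many subjects in both arms needing ACTH tests. Triggers from Visits 6 and 8 are now tested at Visits 7 and 9, among other subjects' tests, and an unscheduled visit would lose that cover. The loss is small, since the current rule already produces otherwise unplanned tests at Visits 4, 5, 6 and 8.

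A reader might infer more than the documents support, in three ways:

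- *That lower-risk subjects are favoured with a prompt unscheduled test.* The ACTH cases in Section 9.2.7 arise at Visit 9 or after early withdrawal, when no main-study visit remains. One of them is an abnormal ACTH test, which is not clearly lower risk. While visits remain, lower-risk subjects wait as well, as the Visit 6 rule shows. Section 9.2.7 shows only that the visit type exists.
- *That treatment must await the test.* Section 7.6.1 says of systemic steroid effects, including adrenal suppression, "If such effects occur, accepted procedures for the management of symptoms should be followed (e.g., treatment with physiologic hydrocortisone, etc". It sits under overdose procedures but does not require a test. Under Section 2.2, "subjects will also be instructed to carry a wallet card identifying the potential risk for AI".
- *That SRC review is blocked.* Section 4.3 lets the Medical Monitor reconvene the SRC at any time, and its examples are not exhaustive.

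**Conclusion.** The point holds as a gap in timing. For a continuing subject with cortisol of 138 nmol/L or lower and features of AI at Visits 3 to 8, the protocol's only explicit timing for the ACTH test is the next scheduled visit. If no other route is used, that is nominally up to 12 to 42 days away, or 8 to 52 days with windows. The other sections permit faster action without requiring it.

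The consequence is possible late confirmation, and with it later referral and a later count towards the SRC example. It is not a bar on testing, treatment or SRC review. The documents do not give the number of subjects who would meet the trigger. Figure 2 and the Laboratory Manual could not be seen and may bear on timing. I would class this as a cheap improvement.

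**What to change.** 1. In Section 9.1.5.1.2, replace the next-scheduled-visit timing with: *at an unscheduled visit as soon as possible and within 7 days of both parts of the trigger being known, or at the next scheduled visit if sooner; clinical management need not await the result*. The 7 days is a proposal for the sponsor's medical team to confirm or shorten. It is just under the shortest permitted gap between these visits (8 days) and has no clinical source in the documents.
2. State whether an unscheduled test triggered from Visit 6 replaces the Visit 7 test under the below-350 rule. Otherwise such a subject is tested twice.
3. Add the case to the Section 9.2.7 list and to the ACTH footnotes of the Schedule of Events.
4. Check Figure 2 and the Laboratory Manual for consistency.

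The cost is wording, an occasional unscheduled visit, and a small possible hint of allocation to site staff, including for triggers from Visits 6 and 8. The test and the visit type already exist. SAP Section 4.4 already accepts ACTH results from unscheduled assessments and assigns them to visits by study day, so it needs no change. If the sponsor meant the present rule as a backstop, the same edit makes that plain.
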